12. SAFETY ANALYSIS

Safety will be evaluated from adverse events (including serious AEs and/or deaths), laboratory results, vital signs, study drug exposure, and concomitant medications. Descriptive statistics will be utilized to summarize these data and will be displayed by treatment arm.

The Intent-to-Treat Population (as Treated) is defined as all enrolled subjects who received any amount of study treatment will be utilized for all safety analyses.

Extra measurements (such as unscheduled or repeat assessments) will not be included in the descriptive statistics but will be included in subject listings.

All AEs, ECG outliers, and clinical laboratory outliers that occur following infusion of study medication will be included in the tabulations of AEs and outlier events, including episodes that occur at unscheduled evaluations.

In addition to the summary tables, safety data will also be presented in the individual subject listings.

12.1 Treatment Emergent Adverse Events

Treatment-emergent adverse events (TEAEs) are defined as all AEs that begin on or after the date of the first administration of study drug. Related to study drug AEs are those reported as possibly related or probably related to study drug. Related to administration AEs are those reported as possibly related or probably related to the study drug administration.

The verbatim terms of the Treatment Emergent Adverse Events (TEAE) will be coded to preferred terms (PT) and system organ classes (SOC) per MedDRA® (Medical Dictionary for Regulatory Activities) Version 23.0.

All reported TEAEs will be listed, documenting all information collected on the eCRF including verbatim term, MedDRA preferred term, MedDRA system organ class, start date, stop date, severity, relationship to study drug, relationship to study drug administration, discontinuation from study, serious, serious criteria, action taken, and outcome.

The TEAEs will be graded by the Investigator in terms of:

- Severity grade:
 - 1=Mild, 2=Moderate, 3=Severe, 4=Life-Threatening, 5=Fatal.
- Relation to CAP-1002 and separately for Administration:
 - “Related” includes events where the causality was reported as “Probable”, or “Possible”, or where the relationship was not reported on the eCRF.
 - “Not Related” includes events where the study drug causality was reported as “Unlikely Related” on the eCRF.

All TEAE summary tables will be presented with the number and percentages of subjects in the Safety population. An overall summary of TEAEs will be tabulated by treatment regimen, relation to Investigational Product relationship to administration, and grade. In addition, TEAEs will be summarized by system organ class (SOC) and preferred term (PT) in descending frequency using MedDRA:

- All TEAEs,
- All TEAEs graded severity,
- All Related TEAEs to Investigational Product,
- All Related TEAEs to Investigational Product graded by severity,
- All Related TEAEs to Study Drug Administration

- All Related TEAEs to Study Drug Administration graded by severity,
- Serious TEAEs,
- Serious and related TEAEs,
- TEAEs leading to discontinuation from study,
- Related TEAEs leading to discontinuation from study,

In the summary tables, subjects may be counted under multiple system organ class (SOC) and preferred terms (PT), but for each SOC and PT category, subjects are only counted once. If a subject has the same AE on multiple occasions, the highest severity grade (fatal > life-threatening > severe > moderate > mild) or drug relationship (probable related > possible related > unlikely) recorded for the event will be summarized. Separate subject listings will be provided for all SAEs, AEs leading to study discontinuation, and deaths.

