## 4 STUDY DESIGN

### 4.1 Overall Design

This is a randomized, double-blind, placebo-controlled study that will enroll subjects with a clinical diagnosis of COVID-19 confirmed by laboratory testing and who are in severe or critical condition as indicated by life-support measures. Prior to protocol procedures, informed consent will be obtained from the subject or a legally authorized representative. Subjects will undergo a screening evaluation to determine eligibility based on the protocol inclusion and exclusion criteria.

Up to 60 subjects will be enrolled and treated in the study. Replacement of non-treated subjects will be allowed with sponsor agreement.

Eligible subjects will be randomized to either the CAP-1002 or placebo group (1:1 ratio) and undergo baseline safety and efficacy assessments approximately 1 to 5 days prior to the administration of investigational product (IP). Treatment administration consists of 1 peripheral IV infusion of IP (█ █ █ for a total of 150M CDCs or matching placebo) administered at the clinical site. Subjects will receive 1 administration of IP on study Day 1. Background standard of care treatment and practices will be maintained for all patients enrolled in the study.

There is no planned dose adjustment. Should an acute toxicity arise during the infusion (e.g., hypersensitivity reaction or pulmonary decompensation), the infusion should be terminated immediately, and the actual total dose administered recorded. Any decision about re-challenging should be made after discussions with the Investigator, Medical Monitor, and other medical experts who may be required to make an informed decision.

A schematic of the protocol design is provided in [Section 1.2](#) and a summary of all activities is provided in [Section 1.3](#).

Subjects will be randomized in a 1:1 allocation to either the CAP-1002 (150M CDCs) or placebo group. See [Section 6.3.1](#) for additional details related to randomization.

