## **8.3 Adverse Events and Serious Adverse Events**

### **8.3.1 Definition of Adverse Events**

An AE is any untoward medical occurrence associated with the use of a drug in humans, whether or not considered drug related. It may be indicated by physical sign, symptom, clinically significant laboratory abnormalities, and/or disease temporally associated with a medical (investigational) treatment, procedure, or product, whether or not related to the medical (investigational treatment, procedure, or product. This definition includes intercurrent illnesses or injuries, exacerbation of pre-existing conditions, or events occurring due to abuse or overdose.

Any condition that was pre-existing is not an adverse event unless there is a change in the nature, severity, or degree of the condition.

Clinical laboratory abnormalities are considered AEs when deemed clinically significant by the Investigator and/or lead to a change in the subject's functional status.

An AE does not include:

- Medical or surgical procedures (e.g., colonoscopy, biopsy). The medical condition that leads to the procedure is an AE.
- Social or convenience hospital admissions where an untoward medical occurrence did not occur.
- Day-to-day fluctuations of pre-existing disease or conditions present or detected at the start of the trial that do not worsen.
- The disease/disorder being studied or expected progression, signs, or symptoms of the disease/disorder being studied unless more severe than expected for the subject's condition.

All Investigators conducting investigative studies supported by Capricor must report both expected and unexpected SAEs to Capricor, or designee, and their individual IRB in compliance with their institutional policies. Please see [Section 8.3.5](#) or further details on AE reporting.

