### **8.3.3      Classification of an Adverse Event**

#### **8.3.3.1      Severity of Adverse Event**

Investigators will monitor all subjects for AEs during the protocol and establish a diagnosis for an event based on signs, symptoms, and/or other clinical information. It is important to distinguish that individual signs and symptoms of the event are not AEs and should not be reported.

For each AE, the Investigator will evaluate the causality and severity, report the action taken, and event outcome and disclose whether or not it caused the subject to discontinue trial participation.

The following severity scale will be used as a guideline to differentiate the severity of adverse events:

- **Mild (Grade 1):** Asymptomatic or mild symptoms; clinical or diagnostic observations only; intervention not indicated.
- **Moderate (Grade 2):** Moderate; minimal, local, or noninvasive intervention indicated; limited age-appropriate instrumental ADL\*.

- **Severe (Grade 3):** Severe or medically significant but not immediately life-threatening; hospitalization or prolongation of hospitalization indicated; disabling; limiting self-care ADL\*\*.
- **Life-Threatening or Disabling (Grade 4):** Life-threatening consequences; urgent intervention indicated.
- **Fatal (Grade 5):** Death related to AE

An AE that is assessed as severe should not be confused with an SAE. Severity is a category utilized for rating the intensity of an event. An event is described as serious when it meets one of the pre-defined outcomes noted in [Section 8.3.2](#). Both an AE and SAE can be assessed as severe. However, an AE of severe intensity may not meet SAE definition requirements.

\*Instrumental ADL refer to preparing meals, shopping for groceries or clothes, using the telephone, managing money, etc.

\*\*Self-care ADL refer to bathing, dressing, and undressing, feeding self, using the toilet, taking medications, and not bedridden.

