### **8.3.4 Time Period and Frequency for Event Assessment and Follow-Up**

All AEs will be reported from the signing of the ICF and are followed by the clinical site until an outcome is known or the subject's participation in the protocol concludes at either the Day 90 or early termination, whichever occurs first.

The clinical site is expected to review all ongoing AEs at each visit. AEs are followed until resolution or until no further changes in the event are expected (i.e., the point at which a subject experiencing an AE is treated successfully and stabilized even though he or she may continue to experience lingering sequelae that may never resolve), or it is agreed that further follow-up of the event is not warranted (e.g., non-serious, IP unrelated, ongoing at final visit). See [Section 8.3.5](#) for reporting ongoing AEs at the end of protocol participation.

For SAEs that were incomplete or ongoing at the time of initial submission, the clinical site is required to submit follow-up SAE Report Forms when event information is available to the research site personnel and/or an outcome is known.

Investigators are not obligated to actively seek information on AEs or SAEs after conclusion of the study participation. However, if the investigator learns of any SAE, including a death, at any time after a participant has been discharged from the study, and he/she considers the event to be reasonably related to the study intervention or study participation, the investigator must promptly notify the sponsor.

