### **8.3.5 Adverse Event Reporting**

All AEs occurring after the initiation of the initial dose of IP will be considered treatment emergent. Any ongoing AE that has not been resolved at the time of protocol completion or early termination for a subject will be marked as ongoing on the Adverse Event Log.

All AEs will be entered in the electronic data capture system (EDC) on to the Adverse Event Log by trained site personnel at the investigative site.

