#### **9.4.9      Exploratory Analyses**

Safety will be evaluated by examining the rates of any SAEs, including Grade 3 or 4 AEs or death that are found to be related or potentially related to CAP-1002 during hospitalization or out 60 days after last treatment. The event rates, their associated 95% confidence intervals, and Kaplan-Meier curves of the times to events will be estimated.

Inferential and descriptive statistics will be used to summarize status measures such as mortality, ICU and hospitalization times, life support measures, and changes in cytokines and biomarkers. Clinical improvement using the median changes from baseline together with shift tables of changes in severity of ARDS and Ordinal Scale of Clinical Improvement will be examined. Multivariable analyses may be performed to estimate the contributions of baseline demographic and risk factors to both safety and efficacy outcomes. Additional inferential statistics may be used for efficacy testing, as appropriate. A detailed description for the statistical methods will be included in the Statistical Analysis Plan for the study.

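### TEAEs are defined by start date alone and the SAP text describes no by-arm count of subjects who worsened, so some deterioration after infusion can be missing from every TEAE table

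*SAP*

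**What the plan says.** - **When AEs are recorded.** Protocol 8.3.4: "All AEs will be reported from the signing of the ICF". The Schedule of Activities places screening and consent on Days -5 to -1.
- **What counts as treatment-emergent.** SAP 12.1: "Treatment-emergent adverse events (TEAEs) are defined as all AEs that begin on or after the date of the first administration of study drug". Protocol 8.3.5: "All AEs occurring after the initiation of the initial dose of IP will be considered treatment emergent". Neither has a clause for events that start earlier and then worsen. The general text of SAP 12 refers to AEs and outliers that follow the infusion.
- **What is not an AE.** Protocol 8.3.1 leaves out the disease under study and "expected progression, signs, or symptoms of the disease/disorder being studied unless more severe than expected". The same section says: "Any condition that was pre-existing is not an adverse event unless there is a change in the nature, severity, or degree of the condition".
- **How worsening was to be shown.** Protocol 9.4.9, under clinical improvement: "shift tables of changes in severity of ARDS and Ordinal Scale of Clinical Improvement will be examined".
- **What the SAP does with those scales.** SAP 11.2 and 11.10 compare mean change by a repeated-measures model. SAP 11.3 counts and tests subjects who improved by at least one point. SAP 14 says that the SAP replaces the protocol's statistical section, and lists no dropped analysis.

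**The concern.** Safety is half of the primary objective, and these are acutely ill inpatients who are not intubated at entry. Respiratory deterioration is therefore an obvious form of harm to look for. Two features of the plan make it harder to see.

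The first is classification. The TEAE tables are the SAP's by-arm counts of adverse events, and the start-date rule keeps out an event that was open at infusion and got worse afterwards.

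The second is counting. Progression judged to be expected creates no AE record. The within-subject tables that would have shown it on the ordinal scale and ARDS severity are not in the SAP text.

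The date rule also makes the SAP disagree with the protocol about Day 1 events.

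**Working it through.** The plan gives no figure to reproduce. The sample size of up to 60 (about 30 per arm) is stated to have no formal calculation. The check is a comparison of rules, followed by simple arithmetic on means.

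**1. The two TEAE rules applied to the same cases**

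| Case | SAP 12.1 | Protocol 8.3.5 | Where it shows |
|---|---|---|---|
| Grade 2 AE starts Day -2; Grade 4 and serious on Day 2; one record | Not a TEAE | Not clearly a TEAE; no worsening clause | SAE listing (SAP 12.2), and death listing (12.4) if fatal; no TEAE table |
| Same, but a new record is opened on Day 2 | TEAE | TEAE | TEAE tables |
| AE starts on Day 1 before infusion | TEAE | Not a TEAE | TEAE tables under the SAP |
| AE starts after infusion | TEAE | TEAE | TEAE tables |

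The first and second rows differ only in how the site records the event. The third row is a direct conflict between the documents.

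**2. Do the documents settle the recording convention?** They do not. Protocol 8.3.4 has sites review open AEs at each visit and follow them to an outcome, which suggests one continuing record. Protocol 8.3.1 makes a changed pre-existing condition an AE, which suggests a new record. It does not say whether an AE that began between consent and infusion counts as pre-existing. Protocol 8.3.3.1 adds that "individual signs and symptoms of the event are not AEs and should not be reported", so a rising oxygen need may be absorbed into an existing diagnosis. The AE fields named in SAP 12.1 include start date, stop date and severity, but no date of grade change.

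**3. Progression.** An SAE is an AE that meets a seriousness criterion (Protocol 8.3.2). Progression judged expected is therefore neither an AE nor an SAE. The exception for progression more severe than expected has no stated criterion, so it rests on the investigator.

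**4. What the SAP text does produce when a subject worsens**
- Ordinal scale: mean change (11.2), AUC (11.4), and number and percentage improved (11.3).
- ARDS severity: mean change (11.10).
- Respiratory support: total time (11.5), not a count of subjects newly ventilated.
- Deaths: survival analysis (11.1) and a listing (12.4).
- Vital signs including SpO2 and respiratory rate, laboratory values, ECG and chest X-ray: summaries by visit (12.5 to 12.8). Unscheduled values are left out of the descriptive statistics, and from Day 7 these assessments are made only in subjects still in hospital.

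No item in the list is a count by arm of subjects who moved to a worse category.

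**5. How far a mean dilutes worsening.** Assume 30 subjects per arm with data. The shift in raw mean change is (subjects × points) / 30.
- One subject from score 4 to 6: 2/30 = 0.07 points.
- One subject from score 4 to 8 (death): 4/30 = 0.13 points.
- Six subjects from score 5 to 6: 6/30 = 0.20 points. Six others improving by one point bring this back to zero.
- One subject with a 10-point fall in SpO2: 10/30 = 0.33 points, though it may show in the reported minimum.

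As an illustration only, a rise in intubation from 4/30 to 10/30 (13% to 33%) is six extra subjects. At one point each, that is the 0.20 above.

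**The case against.** A reader might infer that a deteriorating subject can vanish from all safety output. The documents do not support that. Vital-sign, laboratory, ECG and X-ray summaries need no AE record. The SAE listing is driven by the seriousness flag, with no treatment-emergent restriction. Deaths are both listed and analysed. Progression more severe than expected remains an AE.

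A reader might also set the progression exclusion against Protocol 4.1, which describes acute toxicity during infusion: "e.g., hypersensitivity reaction or pulmonary decompensation), the infusion should be terminated immediately". That is not a contradiction. If such an event is recorded as an AE, it starts on Day 1 and is a TEAE under either rule.

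Other points are fair and limit the claim:
- The Day -2 example fails if sites log worsening as a new record, and the CRF completion rules are not in the documents.
- Counting Day 1 pre-infusion events inflates the TEAE count; it does not hide harm.
- The shift tables were planned under clinical improvement, not as safety tables.
- SAP 8.4 makes the table shells part of the SAP, and they are not in the text available. SAP 9 also makes counts and percentages the default for categorical variables, so a frequency table of scores by visit may exist. It would show each visit's distribution, not who worsened.

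What remains is a TEAE rule with no worsening clause, a Day 1 conflict, and a planned within-subject table dropped without record.

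**Conclusion.** The point holds in bounded form and should be corrected before unblinding. An AE open at infusion that later worsens or becomes serious can be missing from every TEAE table, including the serious ones, when the site keeps a single record. COVID-19 progression judged expected produces no AE. In the SAP text it then shows only in mean-based, duration, mortality, vital-sign and similar routine summaries, where it is diluted but not absent.

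The number of subjects affected cannot be estimated, because the documents give no rate of pre-infusion AEs or of progression. The conclusion assumes that at least some sites carry one record forward and that the unseen shells contain no shift table. If the shells do contain one, the counting part shrinks to a wording gap; the TEAE definition and the Day 1 conflict still need repair.

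**What to change.** 1. **SAP 12.1.** Define a TEAE as an AE that begins, increases in grade or becomes serious after the start of infusion. Where only the date is known, use the date and count the event as treatment-emergent, in line with the convention in SAP 9.4.1 for missing dates. Where the date of change is not captured, have worsening entered as a new AE record. Reconcile the wording with Protocol 8.3.5 and the general text of SAP 12.
2. **SAP 11.2, 11.10 and 14.** Restore the ordinal-scale and ARDS shift tables by arm. Add the number and percentage of subjects, with 95% confidence intervals, who have any worsening from the Day 1 score, and who reach score 6 or higher (including death), by Days 7, 30 and 90. Subjects who have been intubated are excluded at entry, so score 6 or higher is a new event. Record the change in SAP Section 14.

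The ordinal scale is already scored before infusion and at every follow-up visit, so the second item needs no new data. The cost is one or two descriptive tables and some handling of AE records, possibly with a site instruction on logging worsening. Sending every intubation through the SAE process is not needed for this repair; that is a debatable reporting policy and would take a protocol amendment.

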 Follow-up phase will be conducted on Days 2, 3, 7 (± 1 day), 15 (± 1 day), 30 (± 3 days), 60 (± 3 days) and 90 (± 7 days). Follow-up will either be conducted in the inpatient setting or as a phone follow-up should the subject be discharged. Note that as long as the subject remains hospitalized on study the safety of the subject will be monitored on a daily basis per standard of care.

 Data that will collected on a subject-by-subject basis based on occurrence during study participation.

 Prior to baseline assessments on Day 1, Investigator is required to confirm the subject's eligibility based on the inclusion and exclusion criteria in [Section 5.1](#) and [Section 5.2](#).

 Assessment to occur prior to infusion on Day 1.

 Assessment will be conducted in the inpatient setting only if the subject is still hospitalized for this visit.

 Every 15 minutes from pre-infusion through 2 hours post-infusion.

 To capture type of ventilator and respiratory support (e.g., endotracheal ventilator, nasal O2 cannula, face mask, or ECMO) and twice daily SpO2 (%), FiO2 (%) and respiration rate (bpm).

 On treatment day, include immediately pre- and post-infusion.

 Only to be conducted for women of childbearing potential.

 Includes the following clinical laboratory samples: CBC, CMP, CRP, cytokine assay (IL-1, IL-6, TNF- $\alpha$ , INF- $\gamma$ , IL-10), troponin I, myoglobin, ferritin, and procalcitonin.

 Blood samples will be taken and submitted to a central laboratory for future proteomic assay assessment. Information on the assay and procedures for collection and shipping are located in the laboratory manual.

 Subjects will be randomized approximately 1 to 5 days prior to the planned infusion in Treatment Phase to allow enough time for IP ordering and delivery.

-  IP will be ordered approximately 1 to 5 days prior to the infusion (Day 1) in Treatment Phase to allow for enough time for IP delivery. Please see the IP Manual for ordering instructions and timelines.
-  Subjects will be observed for at least 2 hours post-infusion, including vital signs assessments every 15 minutes. The clinical site will observe local institutional policies related to parenteral infusions and post-infusion monitoring. A site Investigator will assess the subject for AEs.

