### **8.2.2 Physical Examination**

The physical examination will be a review of the major organ systems, including general appearance, anthropometrics (height and weight), HEENT (head, eye, ear, nose, and throat), lymphatic, respiratory, cardiovascular, chest, abdomen, gastrointestinal, and musculoskeletal.

Clinically significant findings prior to the start of IP administration are to be captured as medical history.

Clinically significant findings after the start of IP administration are captured and reported as AEs if they meet the definitions of an AE per [Section 8.3.1](#).

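### SAP 12.1 counts treatment-emergent events from the dosing date, Protocol 8.3.5 from the start of dosing, so Day 1 events that precede the infusion are emergent under the SAP only

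*SAP*

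**What the plan says.** Two places define the term.

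- SAP 12.1: "Treatment-emergent adverse events (TEAEs) are defined as all AEs that begin on or after the date of the first administration of study drug". The test is the date; time of day plays no part.
- Protocol 8.3.5: "All AEs occurring after the initiation of the initial dose of IP will be considered treatment emergent". The test is the moment the dose begins.

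A third place, the opening of SAP 12, does not use the term but says what goes into the tables: "All AEs, ECG outliers, and clinical laboratory outliers that occur following infusion of study medication will be included in the tabulations of AEs". The sentence goes on to bring in episodes from unscheduled evaluations.

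Other text bears on the point:

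- Collection starts before dosing (Protocol 8.3.4): "All AEs will be reported from the signing of the ICF".
- Day 1 has a pre-infusion window. In the Protocol 1.3 schedule, the footnote to the Day 1 examination, respiratory status and laboratory tests reads "Assessment to occur prior to infusion on Day 1", and Protocol 8.2.3 places an ECG within 4 hours before the infusion.
- Protocol 8.2.2, on the physical examination: "Clinically significant findings prior to the start of IP administration are to be captured as medical history".
- SAP 12.1 names these fields, among others, for the TEAE listing: "start date, stop date, severity, relationship to study drug". No onset time is named.
- SAP 12.1 treats an event whose relationship was not reported as related.
- SAP 9.4.1 leans towards emergent when a date is missing or partial and nothing contradicts it.
- SAP 1 and SAP 14 say that the SAP overrides the protocol's statistical considerations. SAP 14 lists no change to the TEAE definition.

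**The concern.** A treatment-emergent event is meant to be one that starts once exposure has started. A rule based on the date alone also takes in whatever began earlier on the dosing day. In this trial that window is real: subjects are acutely ill, events are already being recorded, and laboratory tests and an ECG are done shortly before the infusion.

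The protocol and the SAP therefore give different answers for the same record, and neither says that the difference is intended. The precedence clause does not clearly settle it. It refers to statistical considerations, the title of Protocol Section 9, while the TEAE definition is in Section 8.3.5.

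What is at stake is the accuracy of the TEAE tables. Safety is part of the primary objective, and with about 30 subjects per arm one misclassified subject is visible in a table row.

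**Working it through.** The plan states no figure to reproduce. The check is to classify an event by its onset under each text.

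| Onset | SAP 12.1 (date) | Protocol 8.3.5 (start of dose) | SAP 12 tabulation sentence |
|---|---|---|---|
| Before Day 1 | no | no | no |
| Day 1, before infusion | **yes** | **no** | no |
| During infusion | yes | yes | yes, if read as after the start; not named, if read as after the end |
| After infusion | yes | yes | yes |

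1. The two definitions differ in one row, Day 1 before the infusion.
2. That row can hold events. Recording starts at consent, and Protocol 8.3.1 makes a clinically significant laboratory abnormality an adverse event. A new abnormality in the Day 1 pre-infusion sample, or a pre-infusion ECG finding judged to be an adverse event, would fall there.
3. The row is thinned by other rules. Protocol 8.2.2 sends pre-dose examination findings to medical history. Protocol 8.3.1 excludes pre-existing conditions that have not changed, and expected progression of the disease under study. Neither rule empties the row: the first stands in the physical examination section only, and the second leaves new conditions in.
4. An event in this row with blank causality is emergent by the date rule and related by the SAP 12.1 default, so it enters the related-TEAE tables although it precedes exposure.
5. Records without a full start date do not separate the rules in practice. SAP 9.4.1 can set such a start to the dosing date, with no time attached, and the default there is emergent.

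**Size.** The documents give no adverse event rate, so any number rests on assumption. For illustration, assume r new adverse events per subject per day and an infusion at midday (0.5 day of pre-infusion time). The expected number of subjects per arm of 30 with at least one event in the disputed row is 30 × (1 − exp(−0.5r)):

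- r = 0.05: 30 × 0.0247 = 0.74
- r = 0.10: 30 × 0.0488 = 1.46
- r = 0.20: 30 × 0.0952 = 2.85

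These make no allowance for step 3, so they lean high. They also overstate the change in the count of subjects with any TEAE, since such a subject may have a later TEAE anyway. One subject is 1/30 = 3.3 percentage points.

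**The case against.** The strongest reply is that little follows from the mismatch. The date rule applies alike to both blinded arms. It errs towards inclusion, the cautious direction for safety and the one SAP 9.4.1 already takes. SAP 12 plans only descriptive safety summaries, so no test loses power. An event before exposure would normally be rated unlikely related under Protocol 8.3.3.2, which leaves only blank-causality records to reach the related tables. And if the eCRF holds dates only, a fallback that counts unknown timing as emergent gives the SAP's present result. All of this stands and limits the severity. It does not remove a stated rule that labels pre-exposure events as emergent, contrary to the protocol and without a declared change.

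A reader might infer more, and the documents do not support it:

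- *That there are three competing definitions.* Only SAP 12.1 and Protocol 8.3.5 define the term. The SAP 12 sentence is an inclusion statement without a limiting word.
- *That infusion reactions would be lost from the tables.* A reaction during the infusion begins on the dosing date and after the dose has started, so it is emergent under both definitions, and SAP 12.1 specifies the TEAE tables. Losing it would require a strained reading of the SAP 12 sentence to override 12.1.
- *That the mismatch falls on a known single-dose signal.* Protocol 2.2.1 attributes the severe allergic reactions to repeated dosing and reports no signal after single doses. Immunologic reactions remain an anticipated risk (Protocol 8.3.3.3), but that is a weaker statement.

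**Conclusion.** The point holds in a narrow form. The SAP and the protocol define a TEAE differently, the difference is confined to Day 1 onset before the infusion, and it is undeclared. The SAP rule counts those events as emergent and, where causality is blank, as related. The likely result is a slight over-count in both arms of a descriptive table. The comparison between arms is not shown to be biased, and no class of event is shown to be missed. The size cannot be derived from the documents; the figures above depend on an assumed event rate and infusion time. The conclusion that the row can be populated assumes that at least some pre-infusion Day 1 findings are entered on the adverse event log and not as medical history. Severity: minor.

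**What to change.** Four wording changes before database lock:

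1. In SAP 12.1, define a TEAE as an adverse event with onset at or after the start of the infusion, in line with Protocol 8.3.5.
2. For Day 1 events, classify by onset time or by a before/during/after-infusion flag.
3. Where the timing cannot be established, count the event as emergent, consistent with SAP 9.4.1.
4. In the SAP 12 tabulation sentence, replace the reference to events following infusion with events at or after the start of infusion.

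If the sponsor prefers the date rule, SAP 14 should say so and give the reason.

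The cost is a few queries on Day 1 records. SAP 12.1 names no onset time among its listing fields and the eCRF is not available here, so it is unknown how many records already carry a time. Where timing cannot be recovered, the classification does not change. One side effect should be accepted knowingly: a venous-access complication that arises just before the infusion starts would no longer be emergent. It would still appear in the data listings, because SAP 9 lists all data, and the flag would identify it.
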